2.5.9. Overall study evaluation

The authors evaluated the effectiveness of this stratified integrated behavioral health model on diabetes related distress, depressive symptoms, and diabetes outcomes (see measures below) at 6- and 12-month follow-up visits. It was hypothesized that the collaborative behavioral health intervention would produce greater improvement in diabetes related distress, depressive symptoms, as well as HbA1c at 6 and 12 months vs. usual care. A priori analyses were also designed to evaluate mediators of the relationship between improvement in psychological measures (distress/depression) and improvement in HbA1c with the hypothesis that the intervention-associated improvements in diabetes-related distress, regimen related distress, and depressive symptoms would be associated with improvements in A1c in part via association with improvements in self-care behaviors.

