2.5.10. Mid-study Re-assessment and maintenance treatment

At the 6-month mid-study assessment, all patients were re-evaluated using the same measures described below, and either continued to receive twice monthly behavioral sessions (for those with no improvement in distress and depressive symptom scores) as originally assigned at the initial orientation visits, or were transferred to once per month telephonic maintenance follow-up care (for those whose distress and depressive symptom scores improved). Maintenance treatment reinforced prior intervention strategies that produced benefit and provided lifestyle behavioral counseling using elements of the small changes model described above) by the nurse care manager.

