DDS-17 is a 17-item self-reported measure [4] which is designed to indicate a respondent's level of current emotional distress related to diabetes management. Scores are summed and divided by 17 (i.e., mean score) to categorize distress as low, moderate, or high. The DDS-17 also has four subscales, including the Regimen Related Distress sub-score which is an average from five items that assess distress associated with specific treatment and monitoring activities, and which has been correlated with diabetes outcome measures [6,9]. The Satisfaction with Life Scale [25] is a 5-item self-report measure designed to assess satisfaction with a respondent's life as a whole. The study also utilized several previously validated health behavior measures including the Diabetes Empowerment Scale, The Summary of Diabetes Self-Care Activities Measure (SDSCA), the Rapid Eating Assessment for Participants – Shortened Version (REAP-S), and the Duke Activity Status Index, with data collected at baseline, 6-months, and 12-months. The Diabetes Empowerment Scale-Short Form [26] is an abbreviated self-report measure of diabetes-related psychosocial self-efficacy. Dietary habits were assessed using the REAP-S, a 16-item self-report survey [27] designed for use in primary care to directly assess dietary habits for patients with diabetes. Physical activity was assessed by the Duke Activity Status Index, a 12-item self-report measure [28] to assess functional capacity.

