2.6.1. Data analysis plan

All data was collected by project staff via in-person interviews/assessments at all time points and entered into a REDCap database. Demographic and baseline data will be compared between treatment groups; co-variates will be used for any significant differences on subsequent analyses. The principal outcome measure, change in HbA1c, and secondary outcome measures (e.g., change in DDS-17 score, PHQ-9 score, etc.) from baseline to 12 months of follow-up, will be compared (intervention group vs. usual care group) using Students t-test or analysis of variance (ANOVA) as appropriate. The correlation between change in HbA1c and changes in other factors such as DDS-17 score, PHQ-9 score, Diabetes Empowerment Scale Score, etc. will be examined using Pearson Correlation Coefficient. Where appropriate, multivariate analyses including general linear models will be used to further examine the relationship between changes in psychosocial variables and change in HbA1c, (e.g., change in depression or distress and relationship to change in HbA1c) while controlling for demographic characteristics and baseline values. In addition, based on our previous work [11], analyses examining treatment outcomes based on insulin use between the treatment and control groups will be conducted using Students t-test or repeated measures ANOVA. Furthermore, exploratory analyses, including multiple linear regressions, will be examined in the treatment intervention group to examine potential mechanisms for change across time. Missing data at follow-up associated with patients missing assessments will be addressed by using multiple imputations to replace missing values. All variables with <20% of randomly missing data will be kept and imputed. Multiple imputation is preferred because it is superior to other missing data approaches (i.e. mean replacement, last observation) and removing patients with missing data from the study (i.e. list-wise) which would result in a significant loss of the study sample. All analyses will be conducted using SPSS vs. 24 (IBM, Armonk, New York).

REFERENCES

[1] L.E. Barker, K.A. Kirtland, E.W. Gregg, L.S. Geiss, T.J. Thompson, Geographic distribution of diagnosed diabetes in the United States: a diabetes belt, *Am. J. Prev. Med.* 40 (4) (2011) 434–439.

[2] A. Pan, M. Lucas, Q. Sun, et al., Bidirectional association between depression and type 2 diabetes mellitus in women, *Arch. Int. Med.* 170 (21) (2010) 1884–1891.

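### The mechanism analyses, as written, can describe an association with HbA1c change but cannot tie it to the randomized intervention

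*Combined protocol and SAP*

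**What the plan says.** Section 2.5.9 (Overall study evaluation) presents the mediator analyses as a priori. It expects that "the intervention-associated improvements in diabetes-related distress, regimen related distress, and depressive symptoms would be associated with improvements in A1c", with the link running to "improvements in A1c in part via association with improvements in self-care behaviors".

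Section 2.6.1 (Data analysis plan) offers four pieces that bear on this:

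- **Between-arm comparisons:** "secondary outcome measures (e.g., change in DDS-17 score, PHQ-9 score, etc.) from baseline to 12 months of follow-up, will be compared" by t-test or ANOVA. This covers the step from arm to psychological change.
- **Correlations:** "The correlation between change in HbA1c and changes in other factors such as DDS-17 score, PHQ-9 score", among others, by Pearson coefficient.
- **General linear models** of psychosocial change and HbA1c change, where appropriate, "while controlling for demographic characteristics and baseline values". Arm is not among the listed terms.
- **Mechanism regressions:** "exploratory analyses, including multiple linear regressions, will be examined in the treatment intervention group to examine potential mechanisms for change across time".

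The SDSCA is collected at all three visits (section 2.6) but is not named in section 2.6.1. No indirect effect or interval is described.

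Section 2.5.10 makes session frequency after month 6 depend on response. Intervention patients either continue twice-monthly sessions or are "transferred to once per month telephonic maintenance follow-up care (for those whose distress and depressive symptom scores improved").

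Section 2.6.1 also plans an analysis of outcomes by insulin use, using a t-test or repeated measures ANOVA. It names no arm-by-insulin term and no time point for insulin status.

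**The concern.** The hypothesis is about improvements that the intervention brings about. In the intervention arm alone, arm does not vary. A regression there can show that patients whose distress fell also had a larger fall in HbA1c, but patients in usual care might show the same pattern. In a pooled model without arm, two variables that both respond to treatment will correlate even if neither influences the other within an arm.

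In either case an association could be reported as support for the a priori hypothesis when it carries no evidence about a pathway from the intervention. Session frequency adds a further complication: after month 6 it depends on the same symptom change that serves as the predictor.

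**Working it through.** **Inputs from the plan (section 2.4):** HbA1c difference 0.7, alpha 0.05, power 0.80, about 50 per arm needed and about 70 per arm recruited. The SD of HbA1c change is not given, so it has to be back-solved.

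**The plan's own figure.** n = 2(1.960 + 0.842)² SD² / 0.7². Setting n = 50 gives SD ≈ 1.249; the exact t-test gives 1.237. The implied standardized HbA1c effect is 0.7 / 1.237 = 0.566 SD. The stated 50 per arm is therefore consistent with an SD near 1.24, but cannot be confirmed.

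**Assumed, not in the documents:** arm effect on the mediator a = 0.3, 0.5 or 0.8 SD; no link between mediator and HbA1c within arm; 1:1 allocation.

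**Pooled model without arm.** With c = 0.566, the correlation produced by the arm effects alone is

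r = (a·c/4) / √[(1 + a²/4)(1 + c²/4)]

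- a = 0.3: 0.0425 / 1.051 = 0.040
- a = 0.5: 0.0708 / 1.071 = 0.066
- a = 0.8: 0.1132 / 1.119 = 0.101

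The chance of p < 0.05 is about Φ(z√(N−3) − 1.96) + Φ(−z√(N−3) − 1.96), where z is the Fisher transform of r. For a = 0.5 and N = 100, 0.066 × 9.85 = 0.65, giving about 10%. Simulation agrees:

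| Mediator effect | 50/arm, no arm term | 70/arm, no arm term | With arm term |
|---|---|---|---|
| 0.3 SD | 7% | 8% | about 5% |
| 0.5 SD | 10% | 12% | about 5% |
| 0.8 SD | 17% | 22% | about 5% |

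For mediator effects of 0.5 to 0.8 SD, letting the SD of HbA1c change run from 1.0 to 1.5 widens the no-arm range to 8-31%.

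**Does the planned between-arm mediator test protect?** Requiring it to be significant as well gives 3-5% at 0.3 SD, 8% (50/arm) or 11% (70/arm) at 0.5 SD, and 17% or 22% at 0.8 SD. It protects when the mediator effect is small, and much less when the effect is moderate or large.

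**One-arm regression.** Suppose distress change correlates 0.4 with HbA1c change in everyone, but the intervention does not move distress, so the indirect effect is zero. The one-arm regression is then significant in 83% (50/arm) or 94% (70/arm) of trials. It has found a real association, but not one that the intervention produced. A joint test of both steps using both arms is significant in about 5%.

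**What an arm term does not cure.** Assume a mediator effect of 0.5 SD, no other link, and a loss of HbA1c benefit among improved intervention patients after the month-6 change in session frequency. With a loss of 0.4 SD, the arm-adjusted slope is significant in about 10% (50/arm) and 13% (70/arm) of trials. With a loss of 0.57 SD it is about 17% and 21%. The one-arm regression does worse, at 16-21% and 28-37%.

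**Insulin (separate).** Take a true effect of 0.7 in both users and non-users, SD 1.237, and assumed insulin shares of 0.3 to 0.6. With stratum powers p₁ and p₂, the two t-tests disagree on significance with probability p₁(1−p₂) + p₂(1−p₁). This is 50-55% at 50 per arm and 46-54% at 70 per arm. For an interaction of 0.7, SE = SD√(2/k + 2/(n−k)), where k is the number of insulin users per arm. At a share of 0.5 the SE is 0.495 (50/arm) or 0.418 (70/arm). Over the assumed shares, power is about 25-29% and 33-39%.

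**The case against.** - **Arm is unlisted, not excluded.** The plan speaks of general linear models where appropriate, which leaves room for an arm term. A reader might infer that the plan rules arm out; the text does not support that. This point stands.
- **The literal chain in section 2.5.9 runs from psychological change through self-care to HbA1c.** Self-care is the mediator there, and one-arm or pooled models can describe that chain. This also stands, but the improvements are called intervention-associated, and that part needs both arms.
- **The inflation depends on assumed effects.** At 0.3 SD it is slight, and it disappears if the planned mediator comparison is also required. That confines the pooled-model problem to moderate or large mediator effects.
- **SDSCA and the timing of insulin status are missing detail rather than errors.** The list of factors in section 2.6.1 is open-ended, and the baseline list in section 2.6 is a demographic questionnaire, so the absence of insulin there says little. This stands.
- **A reader might infer that the insulin analysis is a faulty test of effect modification.** The plan does not clearly state that aim, and repeated measures ANOVA could test it if the term were specified. The point is therefore conditional.
- **The one-arm regressions are labelled exploratory and the trial's objective is feasibility.** This limits the seriousness. It does not close the gap between an a priori hypothesis and analyses that cannot address its intervention-associated part.

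**Conclusion.** The concern holds in limited form. Followed as written, the mechanism regressions and change-score models can describe associations but cannot connect them to randomization. Leaving arm out of pooled models raises the false-association rate from about 5% to 10-17% (50 per arm) or 12-22% (70 per arm). That assumes mediator effects of 0.5 to 0.8 SD, an HbA1c effect of 0.57 SD from a back-solved SD, and no within-arm link. At 0.3 SD the problem is negligible. The correlations behind these rates are small, 0.10 or less.

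It would be too strong to say that the plan has no between-arm evidence on the mediators, because the 12-month comparisons of DDS-17 and PHQ-9 supply the first step. It would also be too strong to say that an arm term makes the mechanism causal, since confounding and the month-6 change in session frequency remain. The primary HbA1c comparison is not touched. The insulin point is minor and conditional on its aim.

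**What to change.** In section 2.6.1:

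1. Fit the change-score and mechanism models in both arms with an arm term, and name SDSCA as the self-care step.
2. Report the arm-to-mediator and mediator-to-HbA1c estimates as secondary or exploratory, with an indirect effect and confidence interval if wanted. Show the arm-by-mediator term alongside.
3. Label regressions confined to the intervention arm as descriptive.
4. State that mediator-outcome confounding remains. State also that session frequency after month 6 depends on symptom improvement, so that even an arm-adjusted slope on the 6-month mediator can be distorted.
5. Say what the insulin analysis is for. If it is to show whether the effect differs by insulin use, define insulin use at baseline, estimate the arm-by-insulin interaction, give stratum estimates with confidence intervals, and state the low power. A null interaction should not be read as equal effects.

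**Cost:** SAP wording and modest analysis work. The psychosocial, SDSCA and HbA1c data are already collected at baseline, 6 and 12 months. Any interval for an indirect effect has to be combined with the planned multiple imputation. Intervals will be wider, and baseline insulin use may need chart extraction.
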